#### Phone Call

Subjects will be contacted by study team 24h, 48h and six months ( $\pm$  14 days) following their nerve block procedure. The purpose of this call will be to obtain shortness of breath status, potential long term complications and mortality status and document the number of inpatient admissions since the procedure.

#### Blood samples processing:

Some blood samples collected before and after the nerve block (plasma metanephrines, plasma catecholamines, angiotensin II and arginine vasopressin, lactate) will be processed (centrifuged) and stored at -70 degrees Fahrenheit before sent out to an external lab. Storage

duration may vary between weeks to months. Samples will be stored in a research freezer located on the 7th floor of Duke North (cath lab research freezer). As part of the study, we will send blood for study-related laboratory tests to the Mayo clinic and Inter Science Institute. These would include laboratory tests such as metanephrines, vasopressin, catecholamines, and angiotensin. A data transfer agreement is already in place.

Safety endpoints:

- The duration of the anesthetic block is estimated for 12-24 hours. The subject will be monitored for up to 3 hours in the catheterization laboratory/holding area, if there is any concern or evidence of procedure related complications the will be kept overnight in the cath lab holding area. A potentially observed effect of the block to prevent discharge the day of procedure could be orthostatic hypotension. will also be contacted at 48 hours post procedure to ascertain any potentially missed complications. Further the subject's medical chart will be observed for 6 months following study enrollment to evaluate for admissions for heart failure.

Incidence of major side effects has been reported to be <1:1000 and are expected to occur immediately post nerve block. They include:

- Pneumothorax, possibly requiring a chest tube
- Aortic puncture with retroperitoneal bleed or hemothorax
- Spinal cord trauma with possibly paralysis

Incidence of minor side effects like:

- Orthostatic hypotension
- Pain at puncture site and intercostal neuralgia
- Gastrointestinal dysmotility including diarrhea, constipation and abdominal cramping
- Bleeding at puncture site

Efficacy endpoints:

The following efficacy endpoints will be evaluated:

- Primary:
- Improvement in 20 W and peak exercise PA mean and wedge pressure
  - Reduction in central venous pressure and/or pulmonary artery pressure (diastolic) and/or pulmonary capillary wedge pressure at 30 minutes after nerve block

Secondary:

- Reduction in central venous pressure and/or pulmonary artery pressure (diastolic) and/or pulmonary capillary wedge pressure at 30 minutes after nerve block
- Increase in cardiac output at rest, improvement in echocardiographic parameters like ejection fraction (increase), central venous pressure (decrease), pulmonary artery systolic pressure (decrease), right ventricular diameter (decrease), left ventricular diameter (decrease)
- Reduction in pro brain natriuretic peptide (pro-BNP)
- Increase in UOP (output measured in ml/hour) and renal function (BUN and creatinine) in the hours following the procedure.

- Symptomatic improvement like a decrease in dyspnea (dyspnea questionnaire) and 6-minute walk test

Exploratory aims:

- Change in cardiac and autonomic markers after nerve block (i.e. angiotensin and catecholamines)

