### **2. Purpose of the Study:**

Splanchnic vasoconstriction may contribute to decompensation of chronic heart failure via volume redistribution from the splanchnic vascular bed to the central compartment. This is a sympathetically mediated reflex and can be interrupted through a splanchnic nerve block. Therefore, we hypothesize that interruption of the efferent/afferent innervation of the splanchnic vasculature will decrease cardiac congestion and improve renal function in subjects presenting with heart failure.

Objectives:

1. We will determine if splanchnic nerve blockade decreases cardiac preload as measured by invasive hemodynamics.
2. We will determine if splanchnic nerve blockade will improve invasive hemodynamics during exercise.
3. We will determine if splanchnic nerve blockade improves symptoms of shortness of breath.

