### **14. Data Analysis & Statistical Considerations:**

Descriptive statistics of continuous outcomes will include sample size, mean, median, standard deviation, minimum and maximum. For categorical outcomes, the number and percentage of subjects in each category will be presented. Statistical comparisons will be made using t-tests for continuous outcomes and chi square or Fisher's exact test (depending on overall event rates) for categorical outcomes. Paired t-tests will be used to compare changes from baseline to post-intervention. All statistical analyses will be performed using SAS for Windows (version 8.2 or higher) or other widely accepted statistical or graphical software. Subject data listings and tabular and graphical presentations of results will be provided. Unless otherwise specified, a two-sided 0.05 level of significance will be used to declare change in pre- and post-procedure variables different.

For power analysis, our primary endpoint is decreased in central venous pressure following nerve blockade. Based on preliminary animal experiments, we anticipate a reduction of CVP of 25%. For a sample size of 16, If the true difference in the experimental and control means is 25%, we will be able to reject the null hypothesis that the population means of the experimental and control groups are equal with probability (power) .90. The Type I error probability associated with this test of this null hypothesis is 0.05.

There is no direct measure of technical success following attempted block of the splanchnic nerves. The location of the splanchnic nerves is estimated biased on human anatomy dissections and established nerve block protocols used by the anesthesiology department. Procedural success to block the splanchnic nerves will be assumed in 70% of the cases based on the experience in splanchnic nerve blocks in subjects with intractable cancer.

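### The primary endpoint is defined inconsistently between the Efficacy endpoints list and Section 14, and no rule says which or how many pressures must fall

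*Combined protocol and SAP*

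**What the plan says.** The Efficacy endpoints list (Section 4) has two entries under Primary. The first concerns exercise: "Improvement in 20 W and peak exercise PA mean and wedge pressure". That is two pressures at two stages, four measures in all. The second concerns the period after the block: "Reduction in central venous pressure and/or pulmonary artery pressure (diastolic) and/or pulmonary capillary wedge pressure at 30 minutes after nerve block". The same sentence then opens the Secondary list.

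Section 14 introduces its power statement with "our primary endpoint is decreased in central venous pressure following nerve blockade". It expects a 25% reduction and claims power of 0.90 with 16 subjects. It adds that "The Type I error probability associated with this test of this null hypothesis is 0.05".

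Section 14 also sets a default for every variable: paired t-tests for change from baseline, and "a two-sided 0.05 level of significance will be used to declare change in pre- and post-procedure variables different" unless otherwise specified.

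Section 2 lists resting preload, exercise hemodynamics ("We will determine if splanchnic nerve blockade will improve invasive hemodynamics during exercise") and symptoms as objectives, without ranking them.

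**The concern.** A primary endpoint has to tell the reader, before the data are seen, which result decides the trial. Here two sections give different answers, and the longer one contains a list joined by and/or with no success rule. Three gaps follow:

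- The exercise item is listed first under Primary, yet Section 14 neither names it nor powers it.
- The 30-minute item is both primary and secondary.
- Nothing says whether one, several or all of the 30-minute pressures must fall, or whether both Primary items are needed.

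The same data could then be reported as meeting or missing the primary endpoint. In a single-arm trial, a fixed hemodynamic endpoint is one of the main protections against selective reading.

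**Working it through.** **1. The definitions side by side**

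| Measure | Listed as Primary (Section 4) | Listed as Secondary (Section 4) | Primary in Section 14 | Powered |
|---|---|---|---|---|
| PA mean and wedge, 20 W and peak | yes, first | no | no | no |
| CVP at 30 minutes | yes, one of three | yes, same words | CVP, no time given | yes |
| PA diastolic and wedge at 30 minutes | yes, two of three | yes, same words | no | no |

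Two patterns of result separate the readings. If the 30-minute wedge falls and CVP does not, the and/or item succeeds and Section 14 fails. If CVP falls and the exercise pressures do not, Section 14 succeeds, and the trial fails if both Primary items are required.

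**2. The plan's own power figure**

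Inputs from Section 14: n = 16, effect 25%, alpha 0.05 (two-sided by the default), power 0.90. No SD is given, so the figure cannot be reproduced. It can only be solved for the SD that it needs. For a paired t-test, power = 1 − F(t), where t is the 0.975 quantile on 15 degrees of freedom and F is the noncentral t distribution with noncentrality d × √16. Setting power to 0.90 gives d = 0.868, so the SD of change is 25 / 0.868 = 28.8 percentage points. The stated power is attainable, but it covers CVP only.

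**3. False positives for the three-pressure list, no true effect**

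The item says reduction, so significant falls are what count. A two-sided 0.05 test gives a false significant fall 2.5% of the time.

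- Independent pressures: 1 − 0.975³ = 7.3% for a fall in any of three. For change in either direction, 1 − 0.95³ = 14.3%.
- Correlated pressures (simulated paired t-tests, 200,000 replicates, n = 30; n = 16 agrees within 0.3 points):

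| Assumed correlation | Any of three, falls only | Any of three, either direction |
|---|---|---|
| 0 | 7.3% | 14.3% |
| 0.5 | 6.3% | 12.7% |
| 0.8 | 5.0% | 10.0% |
| One pressure only | 2.5% | 5% |

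**4. How often the readings disagree when the block works**

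This compares CVP alone with one possible strict reading: at least one 30-minute pressure and all four exercise measures must fall significantly. Equal effects in all seven measures and equal correlations are assumptions (100,000 replicates).

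| n, effect | CVP alone succeeds | Strict reading succeeds (correlation 0.5 / 0.8) | Opposite verdicts (0.5 / 0.8) |
|---|---|---|---|
| 16, 0.868 SD | 90% | 73% / 80% | 23% / 13% |
| 30, 0.868 SD | over 99% | over 98% | 1.7% / 1.0% |
| 30, 0.5 SD | 75% | 48% / 59% | 36% / 21% |

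The 0.868 SD rows use the effect implied by Section 14 under the paired reading. The 0.5 SD row is a sensitivity case with no source in the documents. Disagreement does not keep growing as the effect shrinks: with no effect, both rules nearly always fail and so nearly always agree.

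**The case against.** The best defense is that CVP is the first-named part of the 30-minute item, so Section 14 merely picks one permitted reading of it. Section 2 calls for invasive measurement of preload, the list gives 30 minutes, and Section 4 describes repeat catheter readings after the block and before exercise. Resting catheter CVP at 30 minutes is therefore a fair inference. This stands, and it makes the conflict with the 30-minute item milder. It does not explain why an exercise item is listed first under Primary, nor why the item containing CVP is also Secondary. If the duplicate is a drafting slip, the reader cannot tell which copy to strike: removing the Primary copy leaves an exercise-only primary, and removing the Secondary copy leaves the and/or.

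The strict reading in step 4 is also only one of several, since the list's layout does not settle how the two Primary items relate. With 30 subjects and the implied effect, the disagreement is small.

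Some stronger readings are tempting but not supported:

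- *That 0.05 is set only for the CVP test.* The default in Section 14 covers every pre/post variable. What is missing is a rule for combining variables and control of the family-wise error.
- *That the echocardiographic CVP is a rival primary.* It is separately labeled within the Secondary list: "improvement in echocardiographic parameters like ejection fraction (increase), central venous pressure (decrease".
- *That any one of all seven measures would count.* The exercise item joins its measures with an and.
- *That the endpoint will be chosen after the results are seen.* The text leaves room for this but does not show it.

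**Conclusion.** The inconsistency is real and nothing in the documents resolves it. The per-variable test is specified. The governing variable, the tier of the 30-minute item and the combining rule are not. Taking any one of the three pressures as success would raise the false-positive rate for a reduction from 2.5% to between 5.0% and 7.3%, or from 5% to between 10.0% and 14.3% if either direction counted.

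With a real effect of the size implied by Section 14, CVP alone and the strict reading would give opposite verdicts in about 23% or 13% of trials at n = 16, and in under 2% at n = 30. A moderately smaller effect would widen the gap. These rates rest on assumed correlations and, for the disagreement figures, on equal effects across measures. The textual conflict rests on none of these.

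A reader might also fold in the missing SD, the two-group wording of the power sentence ("we will be able to reject the null hypothesis that the population means of the experimental and control groups are equal") in an uncontrolled trial, and the 16 subjects against a target of up to 30 in Section 7. Those are separate defects of the power statement. They do not make this point more serious, but they should be repaired when the power line is rewritten.

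**What to change.** State one governing primary endpoint in the same words in the Efficacy endpoints list and in Section 14. For example: change in [pressure] at [rest, 20 W or peak exercise] from pre-block baseline to [time] after the block, by right heart catheter, paired t-test, two-sided 0.05. Delete the and/or wording and place each pressure in one tier only. Resting CVP at 30 minutes is closest to Section 14. An exercise pressure is also admissible, given Section 2 and its first place under Primary. The choice is the sponsor's.

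If more than one pressure is to support a primary claim, state the rule in advance: a fixed order, Holm, or all must fall.

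Restate the power line for the chosen endpoint as a paired comparison, with the assumed effect, the SD of change and the planned number of subjects.

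The cost is wording, a restated power line, and loss of the freedom to claim success on any one pressure. Choosing CVP alone leaves the existing power figure unchanged. Under the implied 0.868 SD effect, Holm over three pressures (worst case alpha 0.05 / 3 = 0.0167) takes CVP power from 90% to 77% at n = 16, and leaves 98% at n = 30. Requiring all three to fall gives 78% to 82% at n = 16 (correlation 0.5 to 0.8). An exercise primary needs its own effect and SD: 90% power requires a mean change of 0.87 SD at n = 16 or 0.61 SD at n = 30.

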## 7. Selection of Subjects:

Subjects will be recruited from Duke University Medical Center outpatient environment. All potential study subjects will be scheduled electively by the cardiologist for a RHC +/- an invasive cardiopulmonary exercise. Subjects will be identified via a routine screen of the outpatient cath schedule weeks ahead of time.

The study will enroll subjects who meet the criteria as detailed below. Potentially eligible subjects will be contacted and informed about the possibility of the study. The actual consent process will occur on the morning of the procedure. The primary enrollment target is up to 30 subjects (15 HF with preserved ejection fraction and 15 HF with reduced ejection fraction).

### Inclusion criteria:

- Age 18-90
- Followed at DUMC for known or suspected diagnosis of HF (NYHA stage 1-3, Class C-D), including subjects on inotropic medication
- Systolic blood pressure (SBP) > 100 mmHg
- Planned for elective diagnostic right heart catheterization

### Exclusion criteria:

#### **Contraindicated medications:**

- Anticoagulation at the time the procedure or in case of recent warfarin use an INR >1.4. Anticoagulation includes: warfarin, or novel oral anticoagulants like dabigatran, rivaroxaban, apixaban, endoxaban or full dose intravenous heparin products or bivalirudin and fondaparinux). Antiplatelet agents besides aspirin such as ticagrelor, prasugrel, Plavix are also considered to be a contraindication if used at time point of procedure.
- Immunosuppressive medications for solid organ transplant

#### **HF medication regimen:**

- Initiation of HF medications (in the 48 hours preceding the study) such as beta blockers, ACEI, ARB, aldosterone receptor blockers, calcium channel blockers of any type, central sympatholytics like clonidine, moxonidine,
- **Recent acute MI or hemodynamic instability:**
  - Acute MI (STEMI or Type I NSTEMI) within 7 days?
  - Evidence of progressive cardiogenic shock within 48 hours
  - Repeat systolic blood pressure <90mmHg or >180mmHg

#### **Certain forms of HF:**

- Restrictive cardiomyopathy
- Constrictive pericarditis
- Pericardial effusion with evidence of tamponade
- Severe valvular stenosis

#### **Severe bleeding risk:**

- Known history of an increased bleeding risk
- Thrombocytopenia (<50,000)

#### **Significant comorbidities:**

- NYHA class symptoms
- End-stage renal disease CKD stage 5 due to primary renal pathology
- Any form of preceding acute or chronic use of ultrafiltration or hemodialysis
- History of thoracic spine surgery
- Severe scoliosis of the thoracic spine
- History of lung surgery or history of pneumothorax or chest tube placement during the current admission
- History of lung disease other than asthma and COPD (like interstitial fibrosis, cystic fibrosis, pneumonitis, lung cancer etc.)
- Respiratory instability (dependent on >4 L nasal cannula for a saturation >90% SpO2)
- Exclude severe pulmonary hypertension
- History of organ transplant (heart, lung, liver, pancreases, small bowel, kidney).

### **Pregnancy**

#### **Procedure**

- Unable to tolerate procedure as determined by subject or investigator
- will be excluded if invasive hemodynamics on study date determine that the subject does not have elevated filling pressures at rest or stress. Following pressures/situations will exclude the subject: wedge pressure <15mmHg (<12mmHg on inotrope) at rest and <25mmHg with peak stress (<22 with inotropes) and greater than the central venous pressure or determined by study personnel to be at risk for nerve block related complications.

### **8. Subject Recruitment & Compensation:**

Potential subjects will be identified via two potential pathways. Research team will screen the outpatient scheduled RHC cases and send a recruitment letter to the subject once their primary care provider has agreed to this. The subject will be contacted over the phone if the subject has not replied to the letter in at least 10 days per policy. The subject will be provided with any additional information he/she wants. In a second scenario the primary provider approaches the study team with a potential cases. In both cases the subject will be given a heads up about being

approached on the day of the study about a second approach in person by a health care provider known to the patient for potential consent.

### **9. Consent Process**

Candidate subjects will be informed of the risks and benefits of participation in the study. They will be informed of the study process and demands. They will be given a copy of the informed consent document to review and afforded adequate time to do so.

Informed consent will be obtained prior to the right heart catheterization. Consent will be obtained by Study PI, Duke Heart Center study coordinators who are trained on the study and who have been trained on Informed Consent Process and other key personnel as designated by the PI. Consent will be obtained in the catheterization laboratory holding area. A subject is considered enrolled in this clinical study at the time at which the subject and investigator or authorized designee have personally signed and dated the Informed Consent Form.

### **10. Subject's Capacity to Give Legally Effective Consent:**

Subject has to be able to understand the English language and understand the study process including all potential risk and benefits to the subject. Any subject where the study personnel or treatment team has cause for concern regarding the subject's ability to understand the study process or follow the consent process capacity, will be excluded from

the study.

**11. Study Interventions:**

- Regional nerve block under fluoroscopic guidance
- Cardiopulmonary exercise
- Lab draws
- Vital signs
- Orthostatic vital signs
- 6-minute walk test
- Non-invasive imaging with ultrasound
- Non-invasive hemodynamic monitoring (heart rate variability, sphygmocor, ReDS, Cheetah Medical)
- Optional: Foley placement

**12. Risk/Benefit Assessment:**

Procedural risks of splanchnic nerve blocks have been extensively studied. Risks associated with this anesthetic nerve block are uncommon. Patients undergoing this procedure have a small risk (<1%) risk of developing local anesthetic systemic toxicity as a complication of regional anesthesia. Symptoms include non-specific central nervous system effects (altered mental status, agitation, seizures) and cardiac arrest. We have now completed 10 cases in the first pilot trial using lidocaine and found no acute or chronic complications.

Mild complications like local pain at injection site, orthostatic hypotension and gastrointestinal dysmotility are time limited and improve with resolution of the anesthetic block. Severe complications like pneumothorax possibly requiring a chest tube, aortic vessel puncture with retroperitoneal bleed or hemothorax and spinal cord injury with possible paralysis. These are very rare since placement of the needle occurs under fluoroscopic guidance.

Other minor risks can include (in order of report in literature and experience at Duke):

- Pain at puncture site and intercostal neuralgia
- Gastrointestinal dysmotility including diarrhea, constipation and abdominal cramping as well as nausea
- Bleeding at puncture site

We will perform the splanchnic block for chronic heart failure, which is a new indication. The splanchnic nerve block has now been studied by us for acute heart failure but not been studied in the setting of chronic disease. We do not expect unexpected side effects other than stated above but unexpected side effects cannot be excluded. For safety purposes subjects enrolled in this study will remain monitored for several hours after the SNB and re-contacted at 48h.

Anticipated benefits to the subject include improvement in central vascular congestion with a reduction in cardiac preload and pulmonary arterial pressures as well as left sided filling pressures. A reduction in cardiac pressures is also likely to improve symptoms of congestion, including shortness of breath.

Further it is expected that a decongestion of the central veins and interruption of the cardiorenal reflex loop will result in an improvement in renal function as measured by urine output. This will further contribute to the decongestion of the subject's vasculature.

While both of those effects are only temporary (12-24h), the benefit provided by the brief episode of decongestion can provide lasting symptomatic improvement. Our intervention serves an additional diagnostic purpose by confirming an increased sympathetic tone in the abdominal innervation and could prompt the treatment team to adjust medical therapy to address the increased sympathetic tone and possible benefit on increased splanchnic capacitance.

